The Mesh-RTL Project for Prevention of Incisional Hernia. Clinical Trial of Non-inferiority to Compare Two Aponeurotic Closure Techniques in Midline Laparotomy in Patients With Elevated Risk for Hernia.

Sponsor: Hospital Regional de Alta Especialidad del Bajío
Responsible Party: Principal Investigator
Investigator: [name] [[name]]
Official Title: Master in clinical research
Affiliation: Hospital Regional de Alta Especialidad del Bajío
Collaborators: [name]
[name]

Approval Number: CI/HRAEB/2018/008

Board Name: Comité de ética en investigación

Board Affiliation: CNBCEI-11-CEI-004-20170731

Friday October 18th 2019

Introduction:

The laparotomy is a surgical incision into the abdomen cavity performed to examine the abdominal and retroperitoneal organs. It is classified according to the medical indication: exploratory, therapeutic, stagemaker, and recently added "damage-control" laparotomy.

There exists so many ways to access the abdominal cavity, usually in relation with the organ or structure to treat; being classified in midline laparotomy, paramedian, transversal, oblique, abdominal-thoracic, etc.

Either an emergency or scheduled procedure, the more usual and functional continues being the midline laparotomy, since it allows a broader and faster approach, with less bleeding and easily to extend if it becomes necessary.

Both the evisceration/eventration and the hernia are considered the most frequent complication of the midline laparotomy with a high morbidity and mortality related. Conditions that will require a second intervention, in Mexico represent the seventh cause of elective surgery and fourth cause of emergency procedures.

So far only the use of the mesh has proven useful in reducing this complication. Our group published in 2016 a clinical trial where it showed that the technique is safe and effective to reduce the presence of incisional hernia, however the use of the mesh brings with it problems such as cost, possibility and use in contaminated cavities and postoperative pain. Therefore, the use of the RTL technique as an alternative means to this will help to have one more option for the management of patients with a high risk of incisional hernia.

Problem Statement:

Does the RTL closing technique in the midline laparotomy has the same incident of herniation than the close with supraaponeurotic mesh in patient with elevated risk?

Justification

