The presence of postincisional hernia need to be considerate as a serious disease, insomuch as it carry on highs rates of morbimortality. The presence of this eventuality is among 0.4-1.2% in elective

surgery and up to 30% in emergency procedures.

It is calculated in de U.S.A. an approximate of 1 million of reinterventions a year to correct this condition, with the respective monetary, time and suffering cost to the patient and the health system.

Given the seriousness, the ultimate global consensus has determinate three main axes to the surgical community to board:

- Identify the relevance of the problem
- Improve the theoretical knowledge and technical capacity in the closing of the abdominal wall
- Implement prophylactic measures in the patients, especially in those with elevated risk.

With the present study we aim to contribute to this global recommendations, comparing two closing techniques of the abdominal wall after a midline laparotomy in patients with elevated risk of herniation. Both techniques are proved safe and useful in other studies, with no comparison to date.

Demonstrate that the use of RTL technique has a similar incidence of herniation than the mesh, in an attempt to prevent postincisional hernias after a midline laparotomy, will bring to the surgical community a cheaper and practical alternative to the mesh.

Objectives:

General:

To determinate if the incidence of post-incisional hernia in patients with high risk after a midline laparotomy are similar between the closure of the abdominal wall with the RTL technique and the supraaponeurotic mesh closure reinforcement.

Specifics:

- To identify the patients with high risk using de validated HERNIA-Project Score.
- To determinate the incidence of post-incisional hernia after one year of the initial midline laparotomy.
- To compare the incidence of post-incisional hernia between the two groups.
- To describe the complications related to each closure technique.

Hypothesis:

Ho Hypothesis:

There is no difference in the incidence of post-incisional hernia between the RTL technique and the reinforcement with supraaponeurotic mesh closure wall.

H1 Hypothesis:

There is difference in the incidence of post-incisional hernia between the RTL technique and the reinforcement with supraaponeurotic mesh closure wall.

Sample size:

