The sample size was calculated according to the formula published by Bouemn et all 2015, and based on the results of Kholer and collaborators 2019, where they found in which a percentage of

success was estimated with the standard treatment of 18.5% compared to the experimental management of 7.2%, with a margin of no less than 3%, with an alpha for a tail of 0.05%, and a beta of 20 %, with a percentage of estimated losses of approximately 10%, a total of 195 patients per group was obtained.

Statistical analysis Data are presented as frequency and percentage, comparisons between groups were using the χ^2 test for binary data or Fisher's exact test. Continuous variables are presented as median and range interquartile range and were compared using the Mann-Whitney U-test or t student test if they meet normal criteria. p-Values of less than 0.05 were considered significant. Statistical analyses were performed with SPSS version 25.0.0. Analysis by intention to treat was used.

Study Type:	Interventional
Primary Purpose:	Treatment
Study Phase:	Phase 4
Interventional Study Model:	Parallel Assignment
	Clinical trial of non-inferiority
Number of Arms:	2
Masking:	Triple (Participant, Care Provider, Investigator)
Allocation:	Randomized
Enrollment:	390 [Anticipated]

Primary Outcome Measure:

1. Incisional Hernia

any abdominal wall gap with or without bulge in the area of a postoperative scar perceptible or palpable by clinical examination

[Time Frame: 12 and 24 months]

Secondary Outcome Measures:

2. postoperative complications

an undesirable and unintended result of an operation affecting the patient that occurs as a direct result of the operation. Haematoma, Facial dehiscence, mesh removal, ileus, reinterventions, re-admissions and death

[Time Frame: 1 month, 1 and 2 years]

Elegibility:

Minimum Age:	18 Years
Maximum Age:	70 Years
Sex:	All
Gender Based:	No

Accepts Healthy Volunteers: Yes

Criteria:

Inclusion Criteria:

- Patients older than 18 years undergoing midline laparotomy, independently of diagnostic or condition, elective or emergency surgery
- Patients with a score equal or greater than 7 of the hernia score
- Patients who accept to participate and sign the informed consent

Exclusion Criteria:

- Patients managed with open abdomen or with the impossibility of close the wall
- Patients who had a previous incisional hernia or patients who are participating in another trial
- Patients with a life expectative less than 12 months

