- Pregnant patients Patients with the antecedent of rejection of prosthetic material

Revised Hernia Score.

$$\text{Revised HERNIA score} = 1 \times (\text{BMI} \geq 25 \text{ kg/m}^2) + (1 \text{ COPD}) + (5 \times \text{extended laparoscopy}) + (6 \times \text{laparotomy}) + (3 \times \text{earlier abdominal operation})$$

The revised HERNIA score was developed and low risk was assigned 0 to 6.9 points, medium risk was assigned 7.0 to 9 points, and high risk was assigned ≥ 9 points.

[figure not shown]
Arms and interventions:

Active Comparator: Onlay Mesh Reinforcement group

The midline fascia was closed with running, slowly absorbable sutures (PDS 1-0) with a recommended suture length to wound length ratio of 4:1. An anterior plane with a width of about 8 cm was created between the anterior fascia and the subcutis. A Lightweight polypropylene mesh was used and placed on the anterior rectus fascia with an overlap of 3 cm. The mesh was fitted in the dissected space and it was fixed with PDS 2-0 suture. Fixing points are placed taking the mesh and the anterior fascia of the rectus muscle, at a distance of 3 cm between each point until completing its circumference.

Experimental: RTL reinforcement group

The RTL suture is placed parallel at a distance of 0.5 cm from the fascial margin. Ideally the thread should lie between the anterior and the posterior rectus muscle sheath; there should be no contact with the rectus muscle. A nonabsorbable monofilament polypropylene thread and a 65-mm $\frac{1}{2}$ needle are used. Around this longitudinal thread, the continuous suture for fascial closure is introduced immediately lateral to the thread; with running, slowly absorbable sutures (PDS 1-0) with a recommended suture length to wound length ratio of 4:1. An anterior plane with a width of about 8 cm was created between the anterior fascia and the subcutis.

References

- Shell DH 4th, de la Torre J, Andrades P, Vasconez LO. Open repair of ventral incisional hernias. Surg Clin North Am. 2008 Feb;88(1):61-83, viii. doi: 10.1016/j.suc.2007.10.008. Review. PubMed ID: 18267162

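### The complications list names mesh removal, which only the mesh arm can have, has no matching item for the permanent RTL thread, and gives no counting rule

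*Combined protocol and SAP*

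**What the plan says.** Under Secondary Outcome Measures, item 2, a complication is first defined in general terms as "an undesirable and unintended result of an operation affecting the patient that occurs as a direct result of the operation". Seven items follow: "Haematoma, Facial dehiscence, mesh removal, ileus, reinterventions, re-admissions and death". The outcome is assessed at three points ("Time Frame: 1 month, 1 and 2 years"). The text does not say whether the seven items are examples or a closed list.

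Under Arms and interventions, the comparator receives a mesh ("A Lightweight polypropylene mesh was used and placed on the anterior rectus fascia with an overlap of 3 cm"), and no mesh is described for the experimental arm. The RTL arm receives a longitudinal thread that is also permanent: "A nonabsorbable monofilament polypropylene thread and a 65-mm" needle are specified.

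The matching specific objective is "To describe the complications related to each closure technique". The Statistical analysis paragraph gives one general rule for binary data, a χ² or Fisher's exact test between groups with p below 0.05 as significant, analysed by intention to treat. It does not say which outcomes are tested, or whether complications are handled item by item, per patient or as a total of events.

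**The concern.** Both techniques leave polypropylene in the abdominal wall, but the list names removal of only one of the two materials. A between-arm comparison of an item is informative only if patients in both arms can have the event and it is recorded in the same way in both. Mesh removal does not meet that condition.

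This is the trial's only safety outcome. RTL is put forward as a cheaper and more practical alternative to mesh, so a reader who accepts non-inferiority on hernia will turn to the complications table next. A small p-value on an item that one arm cannot have, or an event total that counts one mesh problem twice, could be read there as a safety advantage. Harms of the newer technique that are dealt with in clinic could also be missing from the same table.

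**Working it through.** The plan gives no complication rate and no power statement for this outcome, so there is no figure to reproduce. The check takes the three ways in which the list could be analysed, then asks what it captures.

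**Inputs.** 195 patients per arm (Sample size paragraph); χ² or Fisher test with p < 0.05 (Statistical analysis paragraph); the seven listed items. Assumptions: a two-sided test, all 195 patients per arm analysed, and no RTL-assigned patient receiving a mesh. Removal rates are illustrative.

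**1. Mesh removal tested as its own item.** With k removals, all in the mesh arm, Fisher's two-sided p for equal arms is 2 × C(195,k) / C(390,k).

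| Mesh v RTL | p |
|---|---|
| 3 v 0 | 0.248 |
| 4 v 0 | 0.123 |
| 5 v 0 | 0.061 |
| 6 v 0 | 0.030 |

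For k = 6: (195·194·193·192·191·190)/(390·389·388·387·386·385) = 0.0150, and twice that is 0.030. The threshold is crossed at 6/195 = 3.1%. Assumed removal rates of 1%, 3% and 5% correspond to 0.01, 0.03 and 0.05 × 195 = 1.95, 5.85 and 9.75 patients. These are counts of mesh removals, not of bias. They show only that a modest rate is enough to give a significant result on an item where RTL is fixed at zero.

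**2. Events summed.** A mesh removed at re-operation can enter as a mesh removal and as a reintervention: 2 events. A thread removed at re-operation enters as a reintervention: 1 event. Each such pair of equivalent problems adds 2 − 1 = 1 extra event to the mesh arm.

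**3. Patients with any complication.** A mesh removed at a separate operation is already a reintervention, so the item adds 0 patients and no distortion. The opposite extreme is that no mesh removal is counted under any other item. Take a common rate of 10–30% for everything else and a normal approximation with pooled standard error. The chance of a significant result favouring RTL then rises from 2.5% to 4.0–5.1% at a 1% removal rate, 6.3–9.2% at 2%, and 18–32% at 5%. For example, with 20% v 22%:
- pooled SE = √(2 × 0.21 × 0.79/195) = 0.0413
- z = 0.02/0.0413 − 1.96 = −1.48
- probability = 0.07

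This is a bound under assumed rates, not an estimate.

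**4. What the list captures for the thread.** A thread problem needing surgery falls under reinterventions, and one needing admission under re-admissions. One managed in clinic has no named item. The general definition would admit it, so it is lost only if the list is applied as closed.

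**The case against.** The strongest reply is that the plan never specifies the comparison that would be distorted. No composite, total or score is defined. The objective for complications is to describe them, whereas hernia incidence has a separate objective to compare. The χ²/Fisher sentence is generic. Naming a device-specific event is reasonable when the aim is to describe the complications of each technique, and removal of a mesh is a real burden of using one. The general definition is neutral between techniques, and two of the listed items already catch the more serious thread problems. The documents also do not say that clinic removal of this thread occurs, or how often.

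Most of this stands. It rules out saying that thread harm is not captured at all, and it makes any distortion depend on a counting rule that the plan does not give. It does not answer two points: the general test rule does not exempt the item, and a descriptive table is also incomplete if the same kind of event is named for one permanent material and not for the other.

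A reader might go further and infer that the outcome was built to favour RTL, or is tilted that way as a whole. The documents do not support this. The Introduction names among the drawbacks of mesh "possibility and use in contaminated cavities and postoperative pain", yet pain is absent from the complications list. That omission works in favour of mesh, so the net direction across the whole outcome is not established.

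**Conclusion.** The point holds as a gap in definition. One of seven items is specific to the mesh arm, the permanent thread has no counterpart item, and no counting rule is stated. A between-arm test of mesh removal is not interpretable, and at 195 per arm six removals would be enough to make it significant. Summed events could count a mesh re-operation twice. A count of patients with any complication is not distorted by meshes removed at re-operation; what could be missed there is thread problems managed without re-operation or re-admission, if the list is read as exhaustive. Their number cannot be estimated from the documents.

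The conclusion assumes that patients are treated as allocated; under intention to treat, an RTL-assigned patient given a mesh could in principle have the item. The point concerns a secondary outcome only. It is a cheap improvement, not a threat to the trial's main conclusion.

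**What to change.** In Secondary Outcome Measures, item 2, replace mesh removal with: *removal, partial or complete, of the reinforcement material (mesh or RTL polypropylene thread), in theatre or clinic*, recorded in both arms at every complication time point.

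Add two sentences to the Statistical analysis paragraph. First, mesh removal on its own is reported descriptively, without a between-arm test. Second, if any overall complication count is reported, each patient is counted once. The second sentence does not require a new composite endpoint; it applies only if such a total is presented.

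The cost is one line in the outcome definition, two sentences in the analysis text and one extra case report form item. No visit or procedure is added.
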